### **5.3.9 STORAGE**

All storage conditions and specific administration instructions regarding ETR will be provided to the investigator prior to drug delivery at the investigational site. Storage conditions will be mentioned on the label. At the trial site, temperature logging should be performed on a regular basis.

Access to the investigational medication should be restricted to designated trial personnel. The investigator or pharmacist will ensure accountability and appropriate storage conditions of all trial medication used.

At the subject's home, the investigational medication should be stored in the childproof containers and out of reach of younger children and pets.

At the end of the trial, all unused medication will be handled as described in Part II, Section [PART II:3.1](#).

### **5.3.10 ADHERENCE**

Medication adherence is critical to successful antiretroviral therapy. In addition to compromising the efficacy of the current regimen, suboptimal adherence has implications for limiting future effective regimens for patients with resistant strains.

Evidence indicates that adherence problems occur frequently in children and adolescents. Studies have reported that fewer than 50% of children and/or their caretakers reported full adherence to ARV regimens. Although a variety of factors have been associated with adherence, no clear predictors of either good or poor adherence have been consistently identified in children.

The investigator will discuss the importance of good compliance to the entire treatment regimen, including ETR whether taken alone or in combination with other ARVs. It is recommended that the investigator regularly assesses the individual adherence to ETR, as well as all the other ARVs used in combination. If a subject's medication intake is suggestive of inadequate adherence, the investigator should address the issues and help provide solutions to maximize adherence to the therapy. Adherence counseling of the subject/parent(s)/legal representative(s) by the investigator should be documented in the subject's source document/chart.

After termination of data collection (see [Figure 1](#)), treatment adherence counseling should be performed per local standard of care and documented in the subject's medical records only. Data will no longer be recorded in the CRF.

### 5.3.11 PRIOR AND CONCOMITANT THERAPY

All non-ARVs, and all ARVs, which should not be co-administered with ETR are mentioned in Section [PART I:5.3.11.1](#) and Section [PART I:5.3.11.2](#). This list of disallowed medication is based on established or theoretical interactions with ETR. Investigators should refer to the current IB of ETR^1 for an up-to-date overview of disallowed medications during clinical trials with ETR.

For other ARVs to be used in the combination therapy, please consult prescribing information/package inserts and the most current IBs for those individual ARVs as other medications may also be disallowed or cautioned for use given an individual subject's specific situation.

#### 5.3.11.1 Disallowed Non-ARV Medication

For an up to date overview of prohibited medications during trials with ETR please refer to the most current edition of the IB.

The following medications are not allowed from the baseline visit until the end of treatment, or withdrawal visit:

- All investigational medications or investigational vaccines, unless the use was discussed with and approved by the sponsor. An additional requirement for pediatric subjects is the availability of dose recommendations for children;
- Chemotherapeutic agents unless previously allowed by the sponsor;
- All disallowed medication as mentioned in the package insert of ARV drugs included in the OBR.

#### 5.3.11.2 Disallowed ARV Medication

For allowed and disallowed ARVs, please refer to Section [5.3.4](#).

The following ARV drugs are not allowed from baseline onwards and throughout the trial:

- All investigational ARVs, except for emtricitabine [FTC] where this is not licensed yet in a participating country. Another exception, for pediatric subjects, are ARVs approved in adults but not approved for pediatric use, with the exception of tenofovir. Investigational ARVs will be allowed only if favourable pharmacokinetic interaction and safety data exist for co-administration with ETR and the use was discussed with and approved by the sponsor. An additional requirement for pediatric subjects is the availability of dose recommendations for children (e.g. RAL for those age groups where dosing guidelines have been established).
- HIV vaccines;
- NNRTIs (except for ETR);
- PIs other than LPV/rtv, DRV/rtv, ATV/rtv and SQV/rtv for pediatric use. For adults refer to the IB.

## 5.4 Assessments

### 5.4.1 TIMING OF ASSESSMENTS

Subjects will rollover after completion of a previous (parent) trial sponsored by or in collaboration with Janssen Research & Development. Baseline visit will coincide with the last visit of the previous (parent) trial.

Assessments and results from the last visit of the previous (parent) trial will be used for the Baseline visit of this trial; overlapping assessments only need to be conducted once. Additional assessments not included in this protocol can be done locally at the investigator's discretion as per local standard of care.

As subjects roll over from a clinical (parent) trial, a urine pregnancy test is to be performed at the Baseline visit (females of childbearing potential only) and is repeated every 3 months (pediatric subjects) or every 6 months (adult subjects) thereafter.

If a subject is considered eligible after signing of the ICF/Assent, completion of the Baseline Form, and evaluation by the sponsor or its designee, the subject receives the investigational medication (ETR) at the Baseline visit.

It is recommended that subjects be evaluated every 3 months (pediatric subjects) or every 6 months (adult subjects) after starting ETR. A Final/Withdrawal Visit is to be performed.

The exact timing of the assessments is presented in the flowchart in Section 2.

#### **As per Protocol Amendment 3:**

For ongoing subjects, the next planned visit will be a Final/Withdrawal Visit, which will be the last visit with data collection. For new subjects that roll-over from (parent) trial TMC125-C234 (IMPAACT P1090), the next planned visit will be a Baseline Visit which will be performed per local standard of care and documented in the subject's medical records only.

For all new and ongoing subjects, all subsequent visits and assessments will be performed per local standard of care and documented in the subject's medical records only. Investigators will continue to report SAEs possibly related to ETR and pregnancies to the sponsor using regular pharmacovigilance reporting. This information will only be entered in the company safety repository.

For all new and ongoing subjects, if the subject exists the trial, the last visit will be a local standard of care visit but without dispensation of investigational medication.

### 5.4.2 SUBJECT AND DISEASE CHARACTERISTICS

At the baseline visit information will be copied from the previous (parent) trial. **As of Protocol Amendment 3**, this information will be documented in the subject's medical records only for the subjects rolling-over from the TMC125-C234 (IMPAACT P1090) trial.

The overall eligibility of the subject to participate in the trial will be assessed.

### 5.4.3 SAFETY

Safety and toxicity monitoring is performed throughout the trial as per local standard of care.

### 5.4.3.1 Adverse Events/HIV-Related Events

For detailed definitions and reporting procedures of AEs refer to Section 1 in Part II of this protocol. For reported HIV events, further details will be recorded if these events are AIDS-defining illnesses (CDC category C conditions; see 7.3 Addendum 3).

For subjects experiencing specific adverse events, toxicity management should be performed as described in Section 5.5 (Rash Management, and Acute Systemic Allergic Reaction) and Section 5.6 (Hyperglycemia, Hypertriglyceridemia and Hypercholesterolemia, Lactic Acidosis, and Lipodystrophy/Fat Redistribution/Body Changes).

After termination of data collection (see Figure 1), all visits and safety assessments will be performed per local standard of care and documented in the subject's medical records only. Investigators must continue to report SAEs possibly related to ETR and pregnancies to the sponsor using regular pharmacovigilance reporting. This information will only be entered in the company safety repository.

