## PROTOCOL AMENDMENTS

### **Amendment GEN-III (This document)**

**The overall reason for the amendment:** The aim of this roll-over study is to provide continued access to etravirine (ETR) for adult and pediatric subjects who continue to benefit from the use of ETR and who live in a country where ETR is either not commercially available, not reimbursed, or cannot be accessed through another source. As of this amendment, the follow-up in this study will be simplified for the reasons outlined below.

ETR is approved since 2008 in adults and since 2012 in children as of the age of 6 years and has a well-established safety profile. The collection of additional data in Study TMC125-C239 is unlikely to provide substantial additional information on ETR or to impact the risk-benefit assessment. The TMC125-C239 is a roll-over study that has been ongoing since December 2009 and provides already substantial long-term safety information on ETR. The parent trials TMC125-C206 and TMC125-C216 (in adults) ended in August 2008, after which the subjects were able to roll-over in the TMC125-C217 trial and subsequently into this roll-over study. Parent trial TMC125-C213 (in subjects aged 6 to 18 years) ended in August 2011. The parent trial TMC125-C234 (or IMPAACT trial P1090), conducted in subjects aged 1 to 5 years, is still ongoing and subjects still in this trial are expected to roll-over to Study TMC125-C239. By the time of entry in Study TMC125-C239, most of these subjects will have completed 48 weeks of ETR treatment plus an additional few years (up till 5 years) of follow-up in the parent trial. Hence, the subjects from Study TMC125-C239 have been on ETR for a significant amount of time. Therefore, the long-term safety of ETR has been properly assessed in these subjects, thereby allowing the study follow-up to be simplified for all subjects in this roll-over study.

As of this amendment, ETR will continue to be provided through this study until the subject can be switched to locally available ETR-based treatment regimens (ie, commercially available and reimbursed, or accessible through another source [eg, access program or government program]) or to local standard of care, as appropriate.

Furthermore, subjects aged 2 years and older are allowed to roll-over from parent trial TMC125-C234 and dosing instructions are added for pediatric subjects receiving another dose than provided in the dosing chart.

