**The table below gives an overview of the rationale of all changes in the GEN-III amendment and all applicable sections.**

---

**Rationale:** The long-term safety of ETR has been established in patients aged 6 years or more, and the collection of additional data in this study is unlikely to impact the risk-benefit assessment. Therefore, the study follow-up will be simplified, and study-related data will no longer be collected in the Case Report Form (CRF). The information that will continue to be collected consists of serious adverse events (SAEs) possibly related to etravirine and information on pregnancies. These are to be reported to the sponsor using regular pharmacovigilance reporting and will only be entered in the company safety repository. Medical records should be maintained according to the local standard of care and should continue to include details on the use of ETR.

---

[PART I:2 Flowchart](#)

[PART I:4 Trial Objectives](#)

[PART I:5.1.1 Overview of Trial](#)

[PART I:5.1.2 Discussion of Trial Design](#)

[PART I:5.2.5 Removal of Subjects From Therapy or Assessment](#)

[PART I:5.3.10 Adherence](#)

[PART I:5.4.1 Timing of Assessments](#)

[PART I:5.4.3 Safety](#)

[PART I:5.5 Safety Management Guidelines for Cutaneous Events](#)

[PART I:5.6 Toxicity Management for Specific Adverse Events With Concomitant Antiretrovirals](#)

[PART II:1.3 HIV-Related Events or Outcomes](#)

[PART II:1.4 Reporting of Adverse Events](#)

[PART II:3.4 Source Data](#)

[PART II:3.5 Case Report Forms](#)

[PART II:5.1 Reporting](#)

[PART II:8 Data Quality Control/Assurance](#)

---

**Rationale:** To allow continuation of viral suppression, ETR will continue to be provided through this roll-over study until the subject can be switched to locally available ETR-based treatment regimens (ie, commercially available and reimbursed, or accessible through another source [eg, access program or government program]) or to local standard of care, as appropriate.

---

[PART I:4 Trial Objectives](#)

[PART I:5.1.1 Overview of Trial](#)

[PART I:5.2.5 Removal of Subjects From Therapy or Assessment](#)

[PART II:2 Trial Closure Considerations](#)

---

**Rationale:** Inclusion criterion 2 was modified to allow subjects older than 2 years to participate in this roll-over study. Furthermore, dosing instructions were added for pediatric subjects rolling-over from parent trial TMC125-234 who are receiving another dose than the doses provided in the pediatric dosing chart.

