Seven Phase IIb studies (TMC125-C203, -C209, -C223, -C227, -C211, -C229, and -C238 [TEACH]) were completed, in which a total of 486 HIV-1 infected subjects were treated with ETR. In the 2 completed Phase III studies TMC125-C206 and TMC125-C216 (DUET 1 and 2) 599 HIV-1 infected subjects were treated with ETR. The roll-over Phase III study (TMC125-C217) for subjects from the DUET studies who had failed multiple regimens and had limited treatment options left, has also been completed. In total, 503 subjects were treated with ETR in this roll-over study, including 256 ETR treatment-naïve subjects, who were previously treated with DRV + OBR in the placebo arm of the DUET studies, and 247 ETR treatment-experienced subjects, who were previously treated with ETR + DRV + OBR in the ETR arm of the DUET studies. One Phase 4 study TMC125IFD3002 (VIOLIN) is completed.

One Phase II study TMC125-C213 (PIANO) in children as of 6 years of age and adolescents has been completed, in which 101 subjects were treated with ETR. One Phase I/II study TMC125-C234 (IMPAACT P1090) in 26 HIV-1 infected children aged  $\geq 1$  year to  $< 6$  years is ongoing.

The Early Access Program, TMC125-C214, aimed to provide access of ETR to HIV-1 infected subjects who had failed multiple ARV regimens and who had limited treatment options. In total, 5,178 subjects have been treated with ETR in this program, which is now completed. For detailed and updated information on the clinical trial data, refer to the most recent Investigator's Brochure (IB) of ETR.

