### **5.2.2 INCLUSION CRITERIA**

Subjects who meet all of the following criteria are eligible for this trial:

1. Subjects with documented HIV-1 infection.
2. Criterion modified per Amendment 3

- 2.1. Male or female subjects, aged 2 years and older.
3. Subject has successfully completed a clinical (parent) trial with ETR sponsored by or in collaboration with Janssen Research & Development, and continues to receive benefit from the use of ETR.
4. Adult has voluntarily signed the Informed Consent Form (ICF). Pediatric subject (where appropriate, depending on age) and their parent(s) or legal representative(s) have signed the ICF/Assent voluntarily. Children will be informed about the program and asked to give assent (where appropriate, depending on age).
5. Negative urine pregnancy test for females of childbearing potential.

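### For children rolling over from TMC125-C234, Amendment 3 leaves SAEs judged unrelated or doubtful without a clear route to the sponsor, on a safety rationale quantified only from age 6

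*Protocol*

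**What the plan says.** **Rationale.** The table of changes for Amendment GEN-III gives this reason for ending CRF collection: "The long-term safety of ETR has been established in patients aged 6 years or more". The overall reason for the same amendment adds a second argument for the C234 children. It expects that, at entry, "most of these subjects will have completed 48 weeks of ETR treatment plus an additional few years (up till 5 years) of follow-up", counting their time in C234. It concludes: "Therefore, the long-term safety of ETR has been properly assessed in these subjects, thereby allowing the study follow-up to be simplified for all subjects".

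**Population.** Protocol 5.2.2 now admits "Male or female subjects, aged 2 years and older". The Introduction (Section 3) describes "One Phase I/II study TMC125-C234 (IMPAACT P1090) in 26 HIV-1 infected children aged" at least 1 and under 6 years, and says that the trial is ongoing.

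**Data collection.** For new C234 rollovers, Flowchart 2 (2.2) and 5.1.1 place the Baseline Visit and all later visits in local medical records, with no CRF. Under Part II 5.1 the study report holds CRF data, and 5.7.3 plans no analysis after CRF collection ends.

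**Safety reporting.** Section 5.4.3.1 states the reduced rule: "Investigators must continue to report SAEs possibly related to ETR and pregnancies to the sponsor using regular pharmacovigilance reporting". Flowchart 2, the last paragraph of Part II 1.4 and Part II 5.1 repeat it. Earlier paragraphs of Part II 1.4 keep the general rule: every SAE during the trial goes to the sponsor within 24 hours, and the cause of any death is an SAE. On leaving the trial, a paper termination form is shared with the sponsor (2.2, footnote e; 5.2.5).

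**The concern.** The age group with the least prior evidence enters under the thinnest safety collection in the trial. Subjects followed before Amendment 3 had all SAEs, and all adverse events leading to interruption or discontinuation, collected in this study (Flowchart 1; Part II 1.4). The C234 rollovers have neither in a CRF at any point.

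Under the reduced rule, the investigator's view of causality decides whether the sponsor hears of an SAE. Part II 1.2 calls an event doubtful when another drug or disease explains it better. These children have HIV and take background antiretrovirals, so such an explanation is nearly always to hand. One site sees few cases; only the sponsor can compare across sites.

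The sponsor also has a part in their dosing. The dosing chart in 5.3.3 covers age 6 and over. C234 children on another dose may stay on it, with weight adjustment discussed with the sponsor. The sponsor would then join those discussions while receiving safety information already filtered for causality.

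**Working it through.** The plan states no sample size, event rate or precision on this point, so there is no figure to reproduce. The main check sets the texts side by side.

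**1. Route to the sponsor for a C234 rollover**

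| Event | Reduced rule (2.2, 5.4.3.1, end of Part II 1.4, Part II 5.1) | General rule (earlier in Part II 1.4) |
|---|---|---|
| SAE at least possibly related | Reported | Reported within 24 hours |
| Non-fatal SAE, unrelated or doubtful | No route stated | Reported within 24 hours |
| Death judged unrelated or doubtful | Termination form only | Reported within 24 hours |
| Non-serious AE forcing withdrawal (such as a non-serious grade 3 rash, 5.2.5) | Termination form only | AE section of the CRF, which these children do not have |

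**2. Which rule governs.** In 5.4.3.1 and Part II the reduced rule starts once CRF collection has ended. That trigger fits poorly for children who never had CRF collection. Flowchart 2, however, applies the reduced rule in its Baseline column, and 5.1.1 applies it to new and ongoing subjects alike. A site working from Flowchart 2 would not send an SAE judged unrelated; a site working from the general rule would. The text does not say which prevails.

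**3. Ages at entry.** C234 took children from 1 to under 6 years. A child who started at 1 and had 48 weeks (48/52 = 0.92 years) plus the full 5 further years would enter at about 1 + 0.92 + 5 = 6.9 years. One who started at 1 and had only 48 weeks would enter at about 1.9 years, close to the new limit of 2. Rollovers can therefore fall on either side of 6. Their number and ages are not given.

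**4. How thin the prior evidence is (illustration only).** The counts are from the Introduction: 26 (C234), 101 (C213, from 6 years) and 599 (two adult Phase III studies). If no event of some type had been seen, the exact one-sided 95% upper limit on its risk would be 1 − 0.05^(1/n):

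- n = 26: 10.9%
- n = 101: 2.9%
- n = 599: 0.5%

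The chance of seeing no case at true risk p is (1 − p)^n, with p assumed:

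| p | n = 26 | n = 101 |
|---|---|---|
| 1% | 77% | 36% |
| 2% | 59% | 13% |
| 5% | 26% | 0.6% |

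The documents do not say that no events occurred. The zero-event limit only shows what 26 children could exclude at best.

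**The case against.** Several points on the other side have force.

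- **The age-6 sentence is not the only justification.** A reader might infer that the documents claim no long-term safety for the younger children. They do: the amendment's overall reason says it was properly assessed, from exposure in C234. That argument is weak. It speaks of most subjects, gives no safety result and rests on a trial still running. But it is there.
- **Deaths and withdrawals are not wholly lost.** A reader might infer that deaths and unrelated SAEs never reach the sponsor. The documents do not support that. A death or withdrawal ends participation and should produce a termination form, and Part II 1.4 still carries the all-SAE rule. What stands is that the form's content is not described, it is not an expedited report, and the rules conflict.
- **The under-6 group may be small.** Only children still in C234 are expected to roll over, and some may be 6 or older by then. So 26 is a ceiling.
- **The binomial figures do not measure the defect.** A reader might take them as the loss caused by the causality filter. They describe what 26 children can show under complete reporting, and apply equally after the fix.
- **The trial exists to give access.** It tests no hypothesis, the simplification is openly reasoned, and safety reports to authorities and ethics committees continue. This supports leaving the simplification in place for other subjects. It does not settle which SAE rule applies to the C234 children.

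**Conclusion.** The point holds as a conflict between reporting rules, combined with a rationale that is weakest for the children newly admitted. For C234 rollovers, an SAE judged unrelated or doubtful has no clear route to the sponsor. A death, or a withdrawal for a non-serious adverse event, is certain to reach it only on a termination form of undescribed content. None of these children adds CRF data to the mortality and SAE tables in SAP 7.1.

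The size is modest: at most 26 children, taking the Introduction's count as final, and an unknown number under 6 at entry. How many SAEs would be filtered out cannot be estimated, because the documents give no event rate and no split by attribution. The study schematic (Figure 1), which the reduced rule cites for the end of data collection, could not be read here. The conclusion rests on the text and on Flowchart 2.

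**What to change.** Reconcile the passages with a provision limited to C234 rollovers:

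1. All SAEs, including deaths, go to the company safety repository under the existing 24-hour rule of Part II 1.4, whatever the attribution.
2. Adverse events leading to withdrawal for safety reasons are recorded on the termination form already shared with the sponsor, with age, weight and ETR dose at onset. State this in 2.2 (footnote e) and 5.2.5.
3. A line listing of both goes into the existing annual safety report (Part II 5.1).

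The reduced rule must be changed wherever it appears, or new contradictions follow: the title-page summary; 2.2 (Flowchart 2 and the text after it); 5.1.1; 5.1.2; 5.4.1; 5.4.3.1; and Part II 1.3, 1.4, 3.5 and 5.1. The simplification stays as it is for all other subjects, and no dose or treatment rule changes.

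The cost is one short provision carried through ten sections, the added content on the termination form, and slightly more site reporting for at most 26 children on forms already in use. The gain is that the sponsor can form its own view of attribution. With 26 children fully reported, a harm with a 2% risk would still go unseen 59% of the time.
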